7. STUDY PLAN

7.1 Study Schedule

	ICU stay period					ICU discharge	Last FUP
Poractant alfa treated group	Screening ⁷	Day 1 (Randomisation)	Day 2	Day 3	Day 4 – 27	Day X	Day 28
		Before randomisation/treatment and 6-12-24h after each administration up to 72 hours			Every 24h till ICU discharge	Whenever it occurs	
Control group	Screening	Time 72 h			Day 4 – 27	Day X	Day 28
		Before randomisation and at 6, 12, 24, 30, 36, 48, 54, 60, 72 h since randomisation			Every 24h till ICU discharge	Whenever it occurs	
Assessments							
Informed consent	X						
Inclusion and exclusion criteria	X						
Demography	X						

Clinical Study Code No.: CLI-050000-04	Version No.: 4.0
EUDRACT No.: 2020-002632-75 – IND No: 153286	Date: 02 MAR 2021

Poractant alfa treated group	ICU stay period					ICU discharge	Last FUP
	Screening ⁷	Day 1 (Randomisation)	Day 2	Day 3	Day 4 – 27	Day X	Day 28
		Before randomisation/treatment and 6-12-24h after each administration up to 72 hours			Every 24h till ICU discharge	Whenever it occurs	
Control group	Screening	Time 72 h			Day 4 – 27	Day X	Day 28
		Before randomisation and at 6, 12, 24, 30, 36, 48, 54, 60, 72 h since randomisation			Every 24h till ICU discharge	Whenever it occurs	
Vital signs (blood pressure, heart rate)	X	Once Treated group: 24 - 48 - 72h post start of treatment Control group: 24 - 48 - 72h post randomisation			X	X	X
Full physical examination including height and weight	X						
Medical history (SARS COVID-19 ADRS, past and current relevant medical conditions)	X						
Arterial Blood Gas (ABG) Analysis ¹	X (If the screening assessment is done just before randomization no need to repeat the assessment)	Treated group: Before randomisation and 6-12-24h after each administration up to 72 hours Control group: Before randomisation and at 6, 12, 24, 30, 36, 48, 54, 60, 72h since randomisation			Every 24h	X	Once if not discharged from ICU
Respiratory support assessment Ventilator parameters ²	X (If the screening assessment is done just before randomization no need to repeat the assessment)	Treated group: Before randomisation and 6-12-24h after each administration up to 72 hours Control group: Before randomisation and at 6, 12, 24, 30, 36, 48, 54, 60, 72h since randomisation			Every 24h	X	Once if not discharged from ICU

Clinical Study Code No.: CLI-050000-04	Version No.: 4.0
EUDRACT No.: 2020-002632-75 – IND No: 153286	Date: 02 MAR 2021

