12. STATISTICAL METHODS

12.1 Sample Size

A total of 70 patients will be randomised in the study with a ratio 3:2 (i.e. 42 patients randomised to the poractant alfa group and 28 in the control group). Assuming patients in the control arm being free from ventilation on average 1 week (i.e. 7 days), this sample size achieves 84% power to detect a difference of 4 days (i.e. on average 11 ventilation-free days for patients treated with poractant alfa), assuming a standard deviation of 5.5 and a two-sided significance level (alpha) of 0.05 using a two-sample t-test.

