4.1.2.2 Others Secondary Efficacy Variables

- Number of days alive and ventilator-free **at Day 28**
- Mortality **at Day 21 and Day 28**
- Number of days alive and free from invasive ventilation **at Day 21 and Day 28**

- Number of days alive and free from non-invasive ventilation (NIV) at **Day 21 and Day 28**
- Percentage of subjects with improvement in severity status defined as a decrease in the severity score at **Day 28 or Discharge**, whichever comes first. Severity score will be defined as Mild, Moderate, Severe or Death based on PaO₂/FiO₂ ratio and subject status at Day 28 and numerically rated from 1-4 respectively:

Severity	Variable	Criteria
Mild -1	PaO ₂ /FiO ₂ Ratio	200 mmHg < PaO ₂ /FIO ₂ ≤ 300 mmHg
Moderate - 2	PaO ₂ /FiO ₂ Ratio	100 mmHg < PaO ₂ /FIO ₂ ≤ 200 mmHg
Severe - 3	PaO ₂ /FiO ₂	Ratio PaO ₂ /FIO ₂ ≤ 100 mmHg
Death - 4	Patient Status	Yes/No

- Change from baseline in PaO₂/FiO₂ ratio at **6 and 12 hours following administration of each dose** in the treated group and at the similar timepoints in the control group (6, 12, 30, 36, 54 and 60 hours after randomisation)
- Change from baseline in PaO₂/FiO₂ ratio at additional timepoints (i.e. every 24 hours after treatment/randomisation until the subject is discharged from the ICU)
- Percentage of subjects alive and with PaO₂/FiO₂ improvement of >20% at **6 and 12 hours following administration of each dose** in the treated group and at similar timepoints in the control group (6, 12, 30, 36, 54 and 60 hours after randomisation)
- Percentage of subjects alive and with PaO₂/FiO₂ improvement of >20% at the additional timepoints (i.e. every 24 hours after treatment/randomisation till the subject is discharged from the ICU)
- Change from baseline in FiO₂ at **6 and 12 hours following administration of each dose** in the treated group and at similar timepoints in the control group (6, 12, 30, 36, 54 and 60 hours after randomisation)
- Change from baseline in FiO₂ at additional timepoints (i.e. every 24 hours after treatment/randomisation until the subject is discharged from the ICU)
- Length of ICU stay (days) **at Day 28**. Subjects who die or are mechanically ventilated longer than this period are assigned with 28 days
- Percentage of subjects alive and out of ICU **at Day 28**
- Delta SOFA Score and sub-score component measured on **Day 3 and Day 28 or Discharge** whichever comes first

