7.2 Intercurrent Events

Death and Early discontinuation from study drug can be anticipated as intercurrent events:

- Death will be incorporated as a failure outcome for binary endpoints using composite strategy;
- Early discontinuation from study drug will be handled using treatment policy strategy: all data collected after discontinuation from study drug till Day 28 or death will be included;
- Change in respiratory parameters will be analysed using while-alive strategy.

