7.4 Handling of Missing Data

In general, except as described below, missing data will not be imputed.

The number of subjects with missing data will be presented under a “Missing” category. Unless otherwise stated, missing values will not be included in the denominator count when calculating percentages.

When quantitative variables are being summarized, only the non-missing values will be evaluated for calculating summary statistics.

Other critical missing data, if any, will be discussed during the review of the data before database lock. Decisions will be fully documented in the Data Review Report.

Medications: Missing/Incomplete Date

In case of missing or incomplete dates not directly allowing allocation to any category of medications, a worst-case allocation will be done according to the available parts of the start and the stop dates. The medications will be allocated to the first category allowed by the available data, according to the following order:

1. Concomitant medication;
2. Maintained medication;
3. Prior medication.

Procedures: Missing/Incomplete Date

In case of missing or incomplete dates not directly allowing allocation to any category of procedure, a worst-case allocation will be done according to the available parts of the start and the stop dates. The procedure will be allocated to the first category allowed by the available data, according to the following order:

1. Concomitant procedure;
2. Maintained procedure;
3. Prior procedure.

Adverse Events (AEs): Missing/Incomplete Date

In case of missing or incomplete date/time not directly allowing allocation to any of the category of AEs, a worst-case allocation will be done according to the available parts of the start and the stop dates/times. The AE will be allocated to the first category allowed by the available data, according to the following order:

1. Treatment emergent;
2. Pre-treatment.

Adverse Events (AEs): Missing Severity

In case of missing severity, the severity will not be imputed and will be reported as “Missing”. For the table of TEAEs by maximum severity, the maximum severity will be considered as the maximum of the non-missing severities for the relevant subject and preferred term.

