13.2 Reporting Conventions

13.2.1 Treatment and Timepoints Descriptors

In the tables and listings, the treatments, and timepoints will be identified as described below.

Treatment group (as displayed in outputs)	Descriptor for treatment
Poractant Alfa	One or two or three doses of poractant alfa (Curosurf®)
Control	Standard of care

Output	Descriptor for timepoints
Tables and Figures	
For poractant alfa group: Visits: Screening, Day 1, Day 2, ..., Day 28, ICU Discharge.
 
Timepoints: At intubation, Baseline, 6 hours post first dose, 12 hours post first dose, 18 hours post first dose, 24 hours post first dose, 30 hours post first dose, 36 hours post first dose, 42 hours post first dose, 48 hours post first dose, 54 hours post first dose, 60 hours post first dose, 66 hours post first dose, 72 post first dose.
 
For control group: Visits: Screening, Baseline, Day 2, ... Day 28, ICU Discharge.
 
Timepoints: At intubation, Baseline, 6 hours post randomisation, 12 hours post randomisation, 18 hours post randomisation, 24 hours post randomisation, 30 hours post randomisation, 36 hours post randomisation, 42 hours post randomisation, 48 hours post randomisation, 54 hours post randomisation, 60 hours post randomisation, 66 hours post randomisation, 72 hours post randomisation.

Listings and Figures	
For poractant alfa and control groups: Visits: Screening, Day 1, Day 2, ... Day 28, ICU Discharge.
 
Timepoints: At intubation, Baseline, 6 hours, 12 hours, 18 hours, 24 hours, 30 hours, 36 hours, 42 hours, 48 hours, 54 hours, 60 hours, 66 hours, 72 hours.

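### Treated-arm gas-exchange readings follow each dose while control readings follow the clock, so live patients who miss dose 2 or 3 can leave the 30–60 h oxygenation summaries in one arm only

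*Protocol*

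**What the plan says.** **Collection.** In Protocol 7.1 the arterial blood gas and ventilator-parameter rows ask for treated-arm readings "Before randomisation and 6-12-24h after each administration up to 72 hours". The control arm in the same rows is read at 6, 12, 24, 30, 36, 48, 54, 60 and 72 h from randomisation. Protocol 7.2.1.1 and SAP Table 1 repeat this. Two other rows of the schedule do not depend on later doses: treated-arm vital signs are timed from the start of treatment, and mechanistic samples from the first administration.

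**Endpoints.** Protocol 8 and SAP 4.1.2.2 define the early PaO2/FiO2 and FiO2 variables at 6 and 12 h after each dose in the treated arm and "at similar timepoints in the control group (6, 12, 30, 36, 54 and 60 hours after randomisation"). Further readings every 24 h until ICU discharge are also listed.

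**Incomplete dosing.** SAP 13.2.1 describes the treated arm as "One or two or three doses of poractant alfa (Curosurf"), and SAP 10.1 tabulates 1, 2 or 3 administrations. Under SAP 7.2, early drug discontinuation is handled by treatment policy: "all data collected after discontinuation from study drug till Day 28 or death will be included".

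**Counting.** SAP 7.4 does not impute and says that, unless otherwise stated, "missing values will not be included in the denominator count when calculating percentages". SAP 9.3.6 counts patients who die before the timepoint as failures. It then classifies the percentage change as above 20%, or else as 20% or less.

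**The concern.** A treatment-policy strategy needs outcome data after dosing stops. Here the plan names that strategy, but between 24 and 72 h the schedule ties each treated-arm reading to a dose. If the dose is not given, no text requires the reading. A control patient at the same hour is always due to be measured.

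The summaries at 30, 36, 54 and 60 h can then compare treated patients who were still being dosed with all controls still under observation. The control group is not selected in this way, and the selection in the treated group may be related to outcome. Formal testing was dropped (SAP 12), so these descriptive figures are what a reader will have for early oxygenation after the second and third doses. The study also closed short of 70 patients, so each unmeasured patient moves a percentage by more than in the planned arms.

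**Working it through.** **1. The plan's own figure.** The only design calculation concerns the primary endpoint. Protocol 12.1 has "42 patients randomised to the poractant alfa group and 28 in the control group" and says "this sample size achieves 84% power to detect a difference of 4 days", "assuming a standard deviation of 5.5 and a two-sided significance level (alpha) of 0.05 using a two-sample t-test".

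- Standard error = 5.5 × √(1/42 + 1/28) = 1.342; 4 / 1.342 = 2.98.
- Normal approximation: Φ(2.98 − 1.96) = 84.6%. Noncentral t with 68 degrees of freedom: 83.6%.

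The 84% is reproduced. It does not depend on the gas-exchange schedule.

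**2. Which readings depend on which dose** (doses 24 h apart)

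| Control hour | Treated-arm trigger |
|---|---|
| 6, 12, 24 | dose 1 |
| 30, 36, 48 | dose 2 |
| 54, 60, 72 | dose 3 |

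Of the six early timepoints named in the endpoints, 30 and 36 h depend on dose 2, and 54 and 60 h on dose 3. A patient who stops after dose 1 has no required reading at four of the six. One who stops after dose 2 has none at two. The 24, 48 and 72 h values are less exposed, because a separate endpoint is defined every 24 h after treatment or randomisation.

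**3. Effect on the response rate.** Let n be the patients in the arm, s the live patients without a reading, p the response rate among the rest, and q the unobserved rate among the s.

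- Reported rate (SAP 7.4) = p.
- Rate over the whole arm = [p(n − s) + qs] / n.
- Bias = (s/n)(p − q).

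The sign is the sign of p − q. The same formula holds for mean changes, with means in place of p and q.

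**4. Illustration.** The documents give no value for s, p or q. Assume n = 42 and p = 50%:

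| s | Responders / measured | Over 42, all s non-responders | Over 42, all s responders | Largest shift |
|---|---|---|---|---|
| 2 | 20/40 | 47.6% | 52.4% | ±2.4 points |
| 4 | 19/38 | 45.2% | 54.8% | ±4.8 |
| 6 | 18/36 | 42.9% | 57.1% | ±7.1 |
| 8 | 17/34 | 40.5% | 59.5% | ±9.5 |
| 10 | 16/32 | 38.1% | 61.9% | ±11.9 |

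If q = p the bias is zero in every row. Letting p run from 40% to 60% with s up to 10 widens the range to ±14.3 points: (10/42)(0.60 − 0) = +14.3 and (10/42)(0.40 − 1) = −14.3. Deaths stay among the measured non-responders, so s counts live patients only. The actual arm sizes are not given; for the same s, a smaller n gives a larger shift.

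**5. Two counting rules in the SAP.** With s = 6, SAP 7.4 gives 18/36 = 50.0%. Read literally, the else branch in 9.3.6 puts any record with an empty value in the 20%-or-less class. If the six have such records, the rate is 18/42 = 42.9%. The same data then give two answers 7.1 points apart, depending on how the sentence is programmed.

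**The case against.** Several stronger readings are tempting, and the documents do not support them.

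- **That the readings exist only if the dose is given.** Protocol 4.4 has patients who stop treatment asked to continue the remaining visits, and SAP 13.2.1 labels treated-arm timepoints as hours after the first dose, a clock that needs no second dose. What stands is narrower: the reading is not required. The labels are reporting conventions; they also list 18, 42 and 66 h, which neither arm's schedule collects, so they cannot serve as the collection rule.
- **That the response rate is inflated.** A reader might assume 50% response in those who continue and 10% in those who stop; with 10%, 20% or 30% stopping, that gives 4, 8 or 12 points of inflation. The direction there is fixed by the assumption. Dosing is through the endotracheal tube (Protocol 6.2.3), so a patient extubated early may also miss later doses, and losing that patient lowers the rate.
- **That the tables hide the loss.** They do not. SAP 7.8 reports the number of non-missing values and a missing category, Figure 14.2.1 prints the number with results under the axis, and Table 14.3.1 shows doses received. The loss is visible, but the percentage is not corrected for it.
- **That the trial's main result is at risk.** These variables are secondary and, under SAP 7.5 and 12, only described.

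It is also fair to say that SAP 7.11 already allows unscheduled data to be re-allocated, that a new schedule cannot help a closed study, and that a non-responder rule applied to the treated arm alone would merely swap a bias of unknown direction for one against treatment.

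**Conclusion.** The asymmetry is in the text and is worth correcting. Followed as written, the plan can remove live treated patients who stop dosing from the 30, 36, 54 and 60 h summaries in one arm only, which works against its own treatment-policy strategy. The documents settle neither the size nor the direction of any bias. The 7.1-point figure assumes 6 unmeasured patients, an arm of 42, a 50% rate in those measured, and all six responding or none. If patients without a reading respond like the others, there is no bias. The conflict between SAP 9.3.6 and 7.4 needs none of these assumptions. Nothing here affects the days alive and ventilator-free or the stated power.

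**What to change.** 1. **Schedule.** In Protocol 7.1 and SAP Table 1, or in a successor protocol since recruitment has ended, time treated-arm blood gas and ventilator readings at 6, 12, 24, 30, 36, 48, 54, 60 and 72 h after the first dose (after randomisation if never dosed), whether or not later doses are given. The vital-signs row already uses this anchor.
2. **Data in hand.** For SAP 9.3.5 to 9.3.7, fill empty timepoints from unscheduled readings within the ±1 h window, using the re-allocation route in SAP 7.11, with the same rule in both arms.
3. **Table 14.2.9.** Add a supplementary >20% responder rate over all patients alive and in ICU, counting those without a reading as non-responders in both arms. Show the number without a reading by doses received.
4. **Wording.** State in SAP 9.3.6 how a missing value is classified, so that it agrees with 7.4.

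The cost is a few more recorded blood gases in any future study, which controls already have, and one extra presentation in an existing table. That presentation is deliberately conservative: a patient who improved and was no longer sampled would count as a non-responder, so it should stand beside the main rate and not replace it.

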Poractant alfa treated group	ICU stay period					ICU discharge	Last FUP
	Screening ⁷	Day 1 (Randomisation)	Day 2	Day 3	Day 4 – 27	Day X	Day 28
		Before randomisation/treatment and 6-12-24h after each administration up to 72 hours			Every 24h till ICU discharge	Whenever it occurs	
Control group	Screening	Time 72 h			Day 4 – 27	Day X	Day 28
		Before randomisation and at 6, 12, 24, 30, 36, 48, 54, 60, 72 h since randomisation			Every 24h till ICU discharge	Whenever it occurs	
Mechanics Laboratory assessments ³		Treated group: Before randomisation and 12, 24, 48, 72, after first administration Control group: Before randomisation and 12, 24, 48, 72, after randomisation			Treated group: 96h after first administration Control group: 96h after randomisation		
Laboratory assessments ⁴	X			Once Treated group: 24h post last treatment Control group: 72h post randomisation		X	Once if not discharged from ICU
SOFA score ⁵	X			Once Treated group: 24h post last treatment Control group: 72h post randomisation		X	Once if not discharged from ICU
Thoracic CT scan or Chest XR ⁶	X						
Curosurf administration (intreated group)		Three ET administrations with a 24 hours interval (Day 1, Day 2 and Day 3)					
Concomitant Medications	X	X	X	X	X	X	X

Clinical Study Code No.: CLI-050000-04	Version No.: 4.0
EUDRACT No.: 2020-002632-75 – IND No: 153286	Date: 02 MAR 2021

Poractant alfa treated group	ICU stay period					ICU discharge	Last FUP
	Screening ⁷	Day 1 (Randomisation)	Day 2	Day 3	Day 4 – 27	Day X	Day 28
		Before randomisation/treatment and 6-12-24h after each administration up to 72 hours			Every 24h till ICU discharge	Whenever it occurs	
Control group	Screening	Time 72 h			Day 4 – 27	Day X	Day 28
		Before randomisation and at 6, 12, 24, 30, 36, 48, 54, 60, 72 h since randomisation			Every 24h till ICU discharge	Whenever it occurs	
Adverse Events	X	X	X	X	X	X	X
Ventilatory support	X	X	X	X	X	X	X
Concomitant procedures	X	X	X	X	X	X	X

- ¹ Arterial blood gas (ABG) analysis: pH, pCO₂, pO₂, HCO₃, lactate.
- ² Ventilatory parameters: PaO₂/FiO₂, FiO₂, TV (tidal volume), RR (respiratory rate), Cstat (static compliance), Cdyn (dynamic compliance), PEEP (positive end-expiratory pressure), PIP (peak inspiratory pressure), Pplat (plateau Pressure).

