In case the patient will be assigned to the poractant alfa treated group, the treatment must start soon after the randomization (max 2 hr), and within 48hr after intubation

The following procedures for treated group or for control group will be conducted according to the frequencies reported in the above flowchart:

- Treatment procedure for poractant alfa as described in detail in [section 6.2](#). One administration per day with a 24 hours interval
- Arterial Blood Gas (ABG) Analysis
- Ventilatory support
- Ventilatory parameters: PaO₂/FiO₂, FiO₂, tidal volume (TV), respiratory rate (RR), static compliance (Cstat), dynamic compliance (Cdyn), PEEP (positive end-expiratory pressure), PIP (peak inspiratory pressure), Plateau Pressure (Pplat)
- Laboratory assessments for mechanistic analysis: blood sampling and bronchial washings; bronchoscopic washings performed as clinically indicated only, with surplus samples retrieved for mechanistic study as available (for more details ref. to [section 7.2](#))

Clinical Study Code No.: CLI-050000-04	Version No.: 4.0
EUDRACT No.: 2020-002632-75 – IND No: 153286	Date: 02 MAR 2021

- Laboratory assessments: blood count, bilirubin, creatinine, eGFR, LDH, D-dimer, CRP, procalcitonin
- Vital signs will be obtained as appropriate
- SOFA score is calculated considering PaO₂/FiO₂, Glasgow coma scale, mean arterial pressure, and bilirubin, platelet and creatinine levels
- AEs review (including SAEs)
- Concomitant medications and procedure review as applicable

7.1.3 Day 4 – 27 recording:

The following procedures for treated group or for control group will be conducted according to the above flowchart

- Arterial Blood Gas (ABG) Analysis
- Ventilatory support: extubation date recorded (as applicable) and following ventilation procedures recorded
- Ventilatory parameters: PaO₂/FiO₂, FiO₂, tidal volume (TV), respiratory rate (RR), static compliance (Cstat), dynamic compliance (Cdyn), PEEP (positive end-expiratory pressure), PIP (peak inspiratory pressure), Plateau Pressure (Pplat)
- Vital signs will be obtained as appropriate
- AEs review (including SAEs)
- Concomitant medications and procedure review as applicable
- Discharge date from ICU if applicable

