7.2.1 Laboratory assessments

7.2.1.1 Blood Sample Collection (as per [study schedule 7.1](#))

Blood samples (10 mls EDTA and 9 mls for Transfix) will be taken at intubation start as screening evaluation, then 24h after last treatment for poractant alfa group and 72h after randomization for control group. Then at Day 28 or at ICU discharge whichever occurs earlier. In particular:

- *Laboratory analysis*: blood count, bilirubin, creatinine, eGFR, glucose, AST, ALT, LDH, D-dimer, CRP, procalcitonin
- *Arterial blood gas (ABG) analyses*: approximately (~1 ml) of blood sample for the analysis of pH, pCO₂, pO₂, HCO₃, lactate will be taken at screening, before randomisation and 6,12, 24h after each administration up to 72 hours for poractant alfa group; before randomisation and at 6, 12, 24, 30, 36, 48, 54, 60, 72h after randomisation for control group. Then every 24 hours until day 28 or ICU discharge whichever occurs earlier
- *Mechanistic blood laboratory analysis*: inflammatory indices such as cellular and cytokine inflammatory markers and lipid mediators before randomisation and 12, 24, 48, 72, 96h after first administration (while hospitalised) and relative timepoints in the control group since randomization. These analyses are planned only in the UK subpopulation

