10.1 Extent of Exposure

The number of poractant alfa drug administrations (1, 2 or 3) will be presented using frequencies for the poractant alfa group. Actual diluted volume administered (ml) will be summarized using summary statistics.

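### The Day 3 SOFA and safety laboratory assessment is timed from the last dose in the poractant arm but at 72 h in controls, so patients who stop dosing early may be measured sooner than their comparators

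*Protocol*

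**What the plan says.** In Protocol 7.1 (Study Schedule), the SOFA and safety laboratory rows carry one entry in the Day 3 column. It is timed "24h post last treatment" for the treated group and "72h post randomisation" for controls. The next scheduled assessment in both rows is at ICU discharge, or at Day 28 for patients still in ICU. Table 1 of the SAP repeats the schedule. Protocol 7.2.1.1 gives the same rule for blood samples with no reference to Day 3: "then 24h after last treatment for poractant alfa group and 72h after randomization for control group".

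Fewer than three doses is foreseen. SAP 13.2.1 describes the active arm as "One or two or three doses of poractant alfa", and SAP 10.1 states: "The number of poractant alfa drug administrations (1, 2 or 3) will be presented". SAP 7.2, following Protocol 12.3, adds: "Early discontinuation from study drug will be handled using treatment policy strategy". Protocol 4.4 asks that patients who stop treatment be encouraged to stay for the remaining visits.

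Other rows of the schedule use a different clock. Vital signs in the treated arm are timed at 24, 48 and 72 h from the start of treatment, and the mechanistic samples from the first administration.

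**The concern.** Counting from the last dose makes the assessment time depend on how many doses a patient received. That is a post-randomisation event, plausibly linked to tolerance or deterioration, and it can occur in one arm only. Randomisation does not balance it.

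SOFA and laboratory values move over the first days of critical illness. A comparison of 24 or 48 h values with 72 h values therefore mixes any treatment effect with the time course. The outcomes exposed are the change in SOFA score and sub-scores at Day 3 (secondary) and the laboratory summaries (safety). The direction of any distortion cannot be predicted from the documents.

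**Working it through.** The plan states no figure on this timing. Its one design figure, 84% power, reproduces and is not involved: 4 / (5.5 × √(1/42 + 1/28)) = 2.98, which gives 83.6% by the noncentral t with 68 degrees of freedom (84.6% by the normal approximation).

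**Inputs**
- Assessment times: 24 h after last treatment (poractant) and 72 h after randomisation (control); Protocol 7.1 and 7.2.1.1.
- Dosing: "Three ET administrations with a 24 hours interval (Day 1, Day 2 and Day 3" (Protocol 7.1), so 0, 24 and 48 h from first dose.
- Delay to first dose: "the treatment must start soon after the randomization (max 2 hr" (Protocol 7.1.2), so 0 to 2 h.
- Allowed deviation: ±1 h up to 72 h (below the schedule table).
- Study Day: the randomisation date is Day 1 (SAP 7.9.3).

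**Step 1: assessment time after k doses.** The last dose is at 24(k − 1) h, so the assessment is at 24(k − 1) + 24 = 24k h after first dose, or 24k to 24k + 2 h after randomisation.

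| Doses received | Hours after first dose | Hours after randomisation | Nominal difference from control at 72 h | Difference on the randomisation clock | Usual Study Day |
|---|---|---|---|---|---|
| 1 | 24 | 24–26 | 48 h sooner | 46–48 h sooner | 2 |
| 2 | 48 | 48–50 | 24 h sooner | 22–24 h sooner | 3 |
| 3 | 72 | 72–74 | 0 | 0–2 h later | 4 |

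With the ±1 h windows at opposite ends, the one-dose gap could reach 73 − 23 = 50 h.

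**Step 2: does the Day 3 column settle the meaning?** By SAP 7.9.3, 72 h after randomisation is Study Day 1 + 72/24 = 4. So the control value and the three-dose value normally fall on Study Day 4. A two-dose value at 48 h falls on Study Day 3, and a one-dose value on Study Day 2. The column label fits neither reading cleanly, and Protocol 7.2.1.1 has no such label.

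**Step 3: what the outputs would show.** SAP 7.11 presents data at the nominal timepoint, and SAP 9.3.10 and Table 14.2.13 summarise SOFA under Day 3. A 24 or 48 h value filed there would not be visible as early. The laboratory tables take their timepoints from SAP 13.2.1, which counts from first dose. An early value could appear under 24 or 48 h, leaving the 72 h row to patients with all three doses, or it could be filed under 72 h. The documents do not say which.

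**Step 4: effect of a fixed anchor.** At 72 h after randomisation in both arms, the nominal gap is 0 whatever the number of doses. At 72 h after first dose in the treated arm, it is 0 to 2 h.

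**The case against.** The strongest reply is that last treatment means the scheduled third dose. The entry is in the Day 3 column, the endpoint is defined on Day 3, and Protocol 4.4 keeps patients who stop treatment on the remaining visits. On that reading both arms are measured at about 72 h. This is a possible reading and it stands as such. It does not remove the point: 7.2.1.1 carries no Day 3 reference, the column does not match 72 h on the SAP's own day count, and sites could reasonably differ.

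A reader might infer that the anchor contradicts the treatment policy strategy. The documents do not support that. As written, the strategy is a rule on which data are included: observations after discontinuation count, up to Day 28 or death. A value taken at 24 h is still included. The fair statement is that a clock tied to doses received sits poorly with following patients regardless of discontinuation.

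A reader might also infer that no 72 h data could exist for early stoppers. That is too strong. Protocol 7.2.3 describes the laboratory work as part of standard care, and SAP 7.11 allows unscheduled data to be reviewed and re-allocated before lock. Neither guarantees a complete 72 h SOFA score.

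Finally, the final SAP only describes these outcomes (SAP 7.5, 9.3.10 and section 12). No test is biased, because none is made.

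**Conclusion.** The point holds as an avoidable timing difference between arms, of minor importance. On the plain wording, a patient with one or two doses is assessed 48 or 24 h sooner than controls at nominal times; with three doses given on schedule the arms match. This rests on reading last treatment as the last dose received. If sites took it as the planned third dose, no gap arises and only the wording needs repair. A patient randomised to poractant alfa but never dosed has no defined assessment time on the plain reading.

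The number affected cannot be given. The documents contain no early-stop rate, and SAP section 12 reports that recruitment closed before 70, so applying an assumed rate to the planned 42 would not describe the data to be analysed. The consequence is a possibly distorted description of one secondary endpoint and the laboratory tables. The primary and key secondary endpoints and the power are untouched.

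**What to change.** **Schedule (Protocol 7.1 and 7.2.1.1, SAP Table 1).** Time the SOFA and safety laboratory assessment at 72 h after randomisation in both arms, whatever the number of doses received. Alternatively, use 72 h after start of treatment in the treated arm, as vital signs already do, with 72 h after randomisation for a patient who is never dosed. Align the Day 3 label with the chosen time. This is a wording change and adds no assessment.

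**Data already collected.** Identify patients with fewer than three doses from Listing 16.2.5. Show when each Day 3 SOFA and laboratory value was taken, by number of doses received, and flag early values. Listing 16.2.6.3 specifies the assessment date and Study Day for SOFA, not the clock time. Use Study Day there, and hours where they are recorded; nominally, Study Days 2, 3 and 4 separate one, two and three doses, apart from shifts around midnight. Use any available 72 h values through the data review under SAP 7.11, or explain the matter in the study report if the database is locked.

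Do not repeat the summary without the early values. That would remove only the early stoppers, from one arm, and so select on the same post-randomisation event. The cost is some extra table columns or a short listing. If no patient stopped early, one sentence in the study report closes the point for patients who started treatment.
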